## **10. INCLUSION/EXCLUSION CRITERIA**

### **10.1 Inclusion Criteria**

- a) Subjects aged between 18 and 80 years of age at enrolment
- b) Reporting intermittent or persistent low back pain for at least 12 weeks, and/or present at least 50% of the time in the past 6 months
- c) Ability to understand complex motor tasks

## SH-RCT-LBP-US-01 Clinical Investigation Protocol

- d) Ability to interact with a tablet

### 10.2 Exclusion Criteria

- a) Known pregnancy
- b) Submitted to spinal surgery less than 3 months ago
- c) Symptoms and/or signs indicative of possible infectious disorder
- d) Known disorder with indication for spine surgery (i.e., tumor, cauda equina syndrome)
- e) Cancer diagnosis or undergoing treatment for cancer
- f) Cardiac, respiratory or other known disorder incompatible with at least 20 minutes of light to moderate physical activity
- g) Concomitant neurological disorder (e.g. Stroke, multiple sclerosis, Parkinson's disease)
- h) Dementia or psychiatric disorders precluding patient from complying with a home-based exercise program
- i) Illiteracy and/or serious visual or auditory impairment interfering with communication or compliance

Additionally, any patient undergoing a PT program for low back pain will be required to stop ongoing programs to enroll in the study.

### 11. CANDIDATE IDENTIFICATION AND PROCEEDINGS

Candidates will be evaluated at the outpatient musculoskeletal clinic at Emory Orthopaedic and Spine Center (Atlanta, Ga). To centralize all study-related information, a commercially available electronic data capturing (EDC) system will be used. Following the identification of a potential candidate, the investigator will enter the EDC portal and fill the screening survey. If the patient is eligible (i.e. meets inclusion criteria and does not have any exclusion criteria) the investigator will present the study and invite the patient to participate and provide consent.

### 12. PROCESS OF CONSENT

## SH-RCT-LBP-US-01 Clinical Investigation Protocol

The study will be presented verbally to potential participants by a study investigator, in a face-to-face meeting. Adequate time will be allowed for the candidate to clarify any doubts about the study, following which the eConsent form will be sent through the EDC platform to the participant and investigator, for signature. The study consent form (**Annex 1**) will then be signed by the participant and the investigator collecting consent, and stored in the EDC platform.

### **13. ALLOCATION & BLINDING**

Patients will be randomly allocated to one of two groups, using random permuted blocks of 6. After eConsent collection, the investigator will enter the EDC portal and proceed with randomisation (also built into the EDC). Following randomisation, the investigator will contact the person responsible for the rehabilitation program in each group to allocate the participant to the respective study arm. Blinding of investigators and patients regarding allocation arm will not be possible, given the nature of the intervention. Analysis of study results will be performed by a statistician blinded to allocation groups.

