## SH-RCT-LBP-US-01 Clinical Investigation Protocol

### 7. STUDY DESIGN

Prospective, single-center, parallel-group, randomised controlled study.

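### A single block size of 6, printed in the protocol of an open-label, single-centre trial where the enrolling investigator role also randomises, makes allocations partly predictable and leaves an avoidable opportunity for selection bias

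*Combined protocol and SAP*

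**What the plan says.** Section 7 describes the trial as "Prospective, single-center, parallel-group, randomised controlled study". Section 13 says "Patients will be randomly allocated to one of two groups", "using random permuted blocks of 6". The word random there describes the permutation within a block. Only one size is given, no strata are named, and nothing says that the size is withheld from enrolling staff. The allocation ratio is not stated.

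Several steps fall to the investigator role:

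- **Screening and invitation (Section 11).** The investigator fills in the screening survey and, if the patient is eligible, "the investigator will present the study and invite the patient to participate and provide consent".
- **Consent (Section 12).** An investigator presents the study face to face and countersigns the consent form.
- **Randomisation (Section 13).** Once consent is collected, "the investigator will enter the EDC portal and proceed with randomisation".
- **Passing on the arm (Sections 13 and 14.1).** "Following randomisation, the investigator will contact the person responsible for the rehabilitation program in each group". For the digital arm, Section 14.1 assigns the referral to whichever investigator found the candidate.

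Section 13 also states: "Blinding of investigators and patients regarding allocation arm will not be possible". Only the statistician is blinded.

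**The concern.** Concealment depends on the enroller being unable to tell what the next allocation will be. Here the usual sources of predictability come together: one known block size, one running sequence, past allocations that the role learns as part of its work, and the same role deciding on the next invitation. Late in a block, once one arm has its full share, the remaining places are known.

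Eligibility leaves room for judgement. Section 10.1(c) asks whether the patient can understand complex motor tasks. Section 10.2(h) asks whether dementia or a psychiatric disorder would prevent compliance with home exercise. The timing of an invitation is also discretionary. The primary outcome, the ODI at 8 weeks, is self-reported. If patients with better or worse prospects were steered toward one arm, the comparison would be biased. The planned t test, Mann-Whitney test and repeated-measures ANOVA (Section 16) include no prognostic covariates.

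**Working it through.** **Inputs.** From Section 9: N = 102, SD of ODI 17.83, target difference 10 points, power 80%, two-sided 0.05. From Section 13: two arms, block size 6. Assumed: 1:1 allocation (3 + 3 per block), a single sequence, and an enroller who knows the block starts and all earlier allocations. The documents give no figure for predictability.

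**Step 1. The plan's own figure.** A two-sample t test with effect size 10/17.83 needs 50.9 per arm, so 51 per arm, or 102 in all (power 80.1%). The stated total is reproduced. It makes 102/6 = 17 complete blocks.

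**Step 2. Certain allocations.** A 3 + 3 block has C(6,3) = 20 equally likely orders. In 12 of them the last 1 place is certain, in 6 the last 2, and in 2 the last 3.

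- Mean per block: (12×1 + 6×2 + 2×3)/20 = 30/20 = 1.5.
- Share: 1.5/6 = 25%. Over 17 blocks: 25.5 of 102.
- Every block has at least one certain allocation. If the unstated ratio gave a 2:4 split, the share would be 28.9%.

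**Step 3. Best guess.** Always guess the arm with more places left, and toss a coin when they are equal. Over the 20 orders this is right 4.1 times in 6, or 68.3%.

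**Step 4. Several enrollers.** Suppose patients fall at random and evenly to enrollers who see only their own allocations but still know the block starts. Enumeration gives about 3% certain and 58% guessable with two enrollers, and about 1% and 56% with three.

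**Step 5. What steering could do.** Let d be the difference in expected ODI between patients steered to one arm and patients steered to the other. The documents give no value, so 3, 5 and 10 are assumptions. The standard error is 17.83 × √(2/51) = 3.53.

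- Only certain allocations steered: bias = 0.25 × d.
- Every unbalanced point steered, with a suitable patient always at hand: bias = d × (2 × 0.683 − 1) = 0.367 × d. This is the upper case.
- Two-sided error = Φ(−1.96 + bias/3.53) + Φ(−1.96 − bias/3.53).

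| Assumed d | Bias, certain only | True error | Bias, upper case | True error |
|---|---|---|---|---|
| 3 | 0.75 | 5.5% | 1.1 | 6% |
| 5 | 1.25 | 6.4% | 1.8 | 8% |
| 10 | 2.5 | 10.9% | 3.7 | 18% |

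**Step 6. Alternatives** (simulation, 102 allocations, the guesser knows the rule and all earlier allocations).

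| Scheme | Certain | Best guess right |
|---|---|---|
| Fixed blocks of 6 | 25% | 68.3% |
| Random blocks 4/6/8 | about 2.5% | about 68% |
| Big stick, limit 3 | about 16% | about 58% |
| Big stick, limit 5 | about 9% | about 55% |

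Big stick tosses a fair coin until the arms differ by the limit, and then forces the smaller arm. Off the limit nothing can be guessed, so the guess rate for limit 5 is 0.09 + 0.91/2, or about 55%.

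**The case against.** **The plan has real safeguards.** Screening is recorded in the EDC before the invitation, and randomisation is run in the EDC after consent is signed. Nobody can look up the next assignment, and nobody can withhold consent in response to one already issued. That stands. It does not cover inference from earlier allocations before the invitation is made.

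**The 25% is conditional.** Sections 12 to 14.1 refer to investigators in ways that fit several enrollers. If they do not share allocations, predictability falls sharply (Step 4). That stands too. A reader might infer that a quarter of allocations will in fact be known in advance, or that concealment fails outright. The documents support neither, because they do not give the number of enrollers, what each of them sees, or the ratio.

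**The larger bias figures are an upper case.** They require steering at every unbalanced point. The values of d are assumed, and d = 10 equals the trial's whole target difference. Both ends of the range are therefore shown.

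**Some of the bias could be offset.** A reader might infer that no planned analysis could help. Section 16 plans change from baseline and comparisons of baseline variables, so steering on baseline ODI would be partly visible and partly offset. Motivation, expected adherence and other unmeasured prognosis would not be.

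**Varying the block size is a weak remedy for guessing.** This is correct: 4/6/8 leaves the guess rate near 68%. It is an argument about which remedy to choose, not a reason to keep fixed blocks.

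**Conclusion.** The point holds as a design weakness that should be corrected because correction is cheap. The plan prints one block size, and its workflow gives the enrolling role knowledge of past allocations. Under 1:1 allocation, one unstratified sequence and full sight of earlier allocations, 25% of allocations are expected to be certain and 68.3% of best guesses right. With several enrollers working separately, both figures are lower. Possible bias runs from 0.75 to 3.7 ODI points over the assumed steering sizes, with a true two-sided error between about 5.5% and 18%.

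Nothing in the documents shows that anyone would steer patients, so this is not a finding that the trial is biased. The combinatorial figures are exact under their assumptions. The bias figures are illustrations.

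**What to change.** 1. Remove the block size from the protocol given to enrolling staff, and keep the scheme in a restricted randomisation file. State the allocation ratio.
2. Have someone outside the enrolling team generate the list and load it into the EDC.
3. Preferred, if the EDC can take such a list: a maximum-tolerated-imbalance rule, for example big stick with limit 5 (about 9% certain, 55% guessable).
4. Otherwise: randomly varying blocks of 4, 6 and 8. This removes most of the certain allocations (about 2.5% remain) but does not lower the guess rate, so withholding the scheme matters all the more.

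**Cost.** One protocol sentence and a list setting, with no extra patients or procedures. The documents do not say which schemes the EDC accepts, so that must be checked. The downside of limit 5 is a possible final imbalance. With 102 patients the difference must be even, so it is at most 4 (53 against 49), and power is 80.0% instead of 80.1%.

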### 8. STUDY OUTCOMES

#### 8.1 Primary Outcome

Impact on functional disability measured through the Oswestry Disability Index score (patient reported outcome measure) between baseline and 8 weeks.

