### 15. ASSESSMENTS AND SPECIFIC DATA COLLECTION

Patients will be assessed at baseline, 4 and 8 weeks. All questionnaires will be collected through the EDC system. These will need to be filled within 5 consecutive days. To promote compliance with this schedule, whenever the deadline is approaching, automatic email reminders will be sent to participants. Participants will be excluded from the study for protocol breach in case they don't fill in the assessment forms.

Regarding the **baseline assessment**, participants will be asked to complete the survey before the start of the program. This assessment will include all the information pertaining to the primary and secondary outcomes, as well as the following information:

- a) date of birth
- b) gender
- c) height & weight
- d) body mass index
- e) formal education (years of schooling)
- f) job type
- g) baseline physical activity level
- h) previous back surgery (> 3 months ago)
- i) risk factors: working status, smoking status

For the **4- and 8-week assessment**, participants will be required to complete the questionnaire within a 5-day window beginning at the start of week 4 and 8. These assessments will include all the information pertaining to the primary and secondary outcomes. Physical activity will be measured only at baseline and 8 week assessment.

For participants on the digital group, engagement and usage metrics of the educational and CBT components will also be collected automatically.

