## 16. STATISTICAL ANALYSIS PLAN

To assess differences in clinical and demographic variables of the patients allocated to the two study groups, independent samples t test or Mann–Whitney U test will be used for quantitative variables. For categorical variables, Chi-square test or Fisher's exact test will be used.

Outcome analysis will be performed using both an intention to treat analysis and a per-protocol analysis.

The overall impact of the intervention on the primary and secondary outcomes will be assessed considering both the results at the 12-week assessment as well as change from baseline.

Differences between interventions will be evaluated using independent samples t test or Mann–Whitney U test. For non-normally distributed variables, the magnitude of the difference in the medians will be assessed using Hodges-Lehman estimator. Additionally, a repeated measures ANOVA will also be performed, with group as an independent factor and time as a within-subjects factor. When necessary, logarithmic transformation will be performed to obtain normally distributed variables. In all analysis, a significant level of 0.05 will be considered.

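### The self-reported baseline is not required before randomisation, so baseline ODI may be answered with the arm known and can bias change from baseline

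*Combined protocol and SAP*

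**What the plan says.** Sections 11 to 13 describe enrolment as screening by the investigator, consent, then randomisation. No baseline step appears among them. Section 13 states: "After eConsent collection, the investigator will enter the EDC portal and proceed with randomisation (also built into the EDC". The same section says: "Blinding of investigators and patients regarding allocation arm will not be possible, given the nature of the intervention".

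The baseline survey is described only in Section 15, and its timing is tied to treatment: "participants will be asked to complete the survey before the start of the program". For the questionnaires in general, Section 15 adds: "These will need to be filled within 5 consecutive days". On non-completion of the forms it says: "Participants will be excluded from the study for protocol breach".

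Baseline enters the analysis by definition. Section 8.1 gives the primary outcome as: "Impact on functional disability measured through the Oswestry Disability Index score (patient reported outcome measure) between baseline and 8 weeks". Section 16 says outcomes will be "assessed considering both the results at the 12-week assessment as well as change from baseline", and that "a repeated measures ANOVA will also be performed, with group as an independent factor and time as a within-subjects factor". The 12-week visit named there appears nowhere else in the plan; I read it here as the final assessment, and the mismatch is a separate matter.

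**The concern.** A baseline is a fair reference point if it cannot depend on allocation. Here the deadline is the first treatment session, not randomisation. That deadline keeps treatment effects out of the baseline but does not keep out knowledge of the arm. Someone who has just been assigned the arm they wanted, or did not want, may rate disability and pain differently. No section says when the participant is told the arm, and none withholds it until baseline is complete.

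The exposed measures are the self-reported ones: ODI, pain, work productivity, interest in surgery, medication use, fear-avoidance beliefs, GAD-7, PHQ-9 and the physical activity questionnaire. Engagement and satisfaction are not affected. The blinded statistician in Section 13 does not help, because the bias would already be in the patient's answer.

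There is a smaller second consequence. If baseline follows randomisation, the Section 15 exclusion rule turns a blank baseline form into a post-randomisation exclusion, which may be selective by arm. If baseline comes first, that route does not exist.

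**Working it through.** **Order of events**

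| Step | Where | What must come before it |
|---|---|---|
| Screening survey, filled in by the investigator | Section 11 | Identification of a candidate; no ODI is mentioned |
| Consent | Section 12 | Eligibility |
| Randomisation | Section 13 | Consent only |
| Contact with the programme lead | Section 13 | Randomisation |
| Therapist assigned, onboarding contact (digital arm) | Section 14.1 | Allocation |
| Programme start | Section 15 | Baseline survey |

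Both consent–baseline–randomisation–start and consent–randomisation–baseline–start satisfy every stated rule. In the second order there is a built-in interval in which the arm can be known, and a digital participant knows it by onboarding at the latest.

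**The plan's own figure.** Section 9 gives SD 17.83, a 10-point difference, 80% power and two-sided 0.05. The standardised difference is 10/17.83 = 0.561. The two-sample t test needs 50.88, so 51 per arm and 102 in total, which matches Section 9. The present point does not change that number.

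**Effect of an arm-related baseline shift.** From the documents: SD 17.83 and a total of 102. Assumed: 1:1 allocation (51 per arm), the same SD at each visit, no true treatment effect, correlation r = 0.3, 0.5 or 0.7 between visits, a differential baseline shift of d points, and a share k of that shift still present at week 8.

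- Bias in the difference in mean change = d(1 − k), in absolute value.
- SE = 17.83 × √(2(1 − r)) × √(2/51) = 4.18, 3.53 and 2.74 for r = 0.3, 0.5 and 0.7.
- False-positive rate: two-sided t test with 100 df and noncentrality d(1 − k)/SE. Example: d = 3, k = 0, r = 0.5 gives 3/3.53 = 0.85 and a rate of 13.4%.
- Group-by-time F test over baseline, 4 and 8 weeks, compound symmetry, shift at baseline only: df 2 and 200, noncentrality 51d²/(3 × 17.83² × (1 − r)). Example: d = 3, r = 0.5 gives 459/476.9 = 0.96 and a rate of 12.8%.

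False-positive rates (nominal 5%), ranges over r = 0.3 to 0.7:

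| Shift d | Change score, none persists | Change score, half persists | Change score, all persists | Group-by-time, baseline only |
|---|---|---|---|---|
| 2 points | 7.6–11.2% | 5.65–6.5% | 5% | 7.3–10.7% |
| 3 points | 11.0–19.2% | 6.5–8.4% | 5% | 10.5–18.6% |
| 5 points | 22.0–44.1% | 9.1–14.8% | 5% | 21.4–45.1% |

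A 1-point shift that fades entirely gives 5.65–6.5%, because its bias equals that of a 2-point shift of which half persists. A simulation of 40,000 trials for d = 3, k = 0 gave 10.9%, 13.2% and 19.4%, against calculated values of 11.0%, 13.4% and 19.2%.

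**Could the analysis repair it?** The planned comparison of follow-up values does not use baseline and stays at 5% under a baseline-only shift. Adjusting for baseline, which Section 16 does not specify, would still carry a bias of about r × d. For d = 3 that is 0.9 to 2.1 points, with a false-positive rate of about 5.8–13.2% (normal approximation).

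**The case against.** The strongest reply is that the plan is silent rather than wrong. Randomisation after consent does not mean straight after consent, and a site that takes baseline at the consent visit complies fully. The consent form was not available for this review and might describe the order. This is why the point is put as a missing requirement and not as a claim that baseline will be late. What the consent form might say is conjecture, and the sections that govern randomisation and assessment do not impose the order.

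The second reply concerns size. The plan supports no value for the shift, its direction, its persistence or the correlation, and the results run from 5% to about 45%. The upper end needs a 5-point differential shift, half of the 10-point difference in Section 9, that is gone by week 8. Participants also know their arm at follow-up, so some of the tendency could persist, which pulls the rate back towards 5%. All of this stands: the table shows how the bias works and does not forecast it.

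Third, knowledge of the arm when follow-up is self-reported is the larger limit of an open-label design, and this change does not touch it. That is true, but that limit is unavoidable, whereas an allocation-aware baseline is avoidable.

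Fourth, the exclusion point holds only if baseline comes after randomisation, and Section 16 plans an intention-to-treat analysis. It is therefore conditional and adds little weight.

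**Conclusion.** The concern holds as a gap in the required sequence. Two of the planned analyses, change from baseline and the group-by-time term, are open to a bias that cannot reliably be removed afterwards: without a value taken before allocation, an arm-related shift cannot be told apart from chance imbalance. How much it matters depends on unknowns, chiefly how large the shift is and how much of it fades. Under the stated assumptions, a fully fading shift of 2 points, one fifth of the difference used for the sample size, would roughly one-and-a-half-fold to double the false-positive rate of the change-score test. Confidence is medium, because actual site practice may already be sound. The change should be made because it is cheap and closes the route completely.

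**What to change.** Add to Sections 13 and 15: 'The baseline questionnaires are completed in the EDC after eConsent and before randomisation; the EDC releases the randomisation function only once the baseline ODI and other baseline forms are complete.'

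This removes allocation-aware baselines and the missing-baseline route to post-randomisation exclusion. It does not deal with exclusion for blank forms at weeks 4 and 8, which needs its own correction.

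The cost is one sentence and one gating rule, since randomisation and the questionnaires already share the EDC. The sample size stays at 102. Randomisation may wait a few days when forms are not completed at the consent visit. If the site already works in this order, the sentence simply records it.

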### **14. INTERVENTION**

#### **14.1 Digital program**

Patients in the digital intervention group will benefit from an 8-week program composed of therapeutic exercise, education and cognitive behavioural therapy (CBT) program provided by SWORD Health. These patients will be referred to SWORD Health by the investigator who identified the candidate. SWORD Health will then assign a physical therapist to each patient. The physical therapist will contact the patient for onboarding and will manage the case.

Patients in this group will perform home-based rehabilitation sessions using SWORD Phoenix®, under remote monitoring by a PT. Participants will be provided with a tablet computer with a SWORD mobile app installed, along with two inertial motion trackers (each comprised of a gyroscope, an accelerometer and a magnetometer) to be placed on the upper and lower back,

